### 6.3 Harms

Within this trial the following definitions of adverse events will be used:

#### **Device Deficiency (DD)**

Inadequacy of a medical device with respect to its identity, quality, durability, reliability, safety or performance.

Note: Device Deficiencies include malfunctions, use errors, and inadequate labelling. All Device Deficiencies that could have led to a Serious Adverse Device Effect shall be reported in accordance with Serious Adverse Event reporting procedures.

#### **Adverse Event (AE)**

Any untoward medical occurrence, unintended disease or injury, or untoward clinical signs (including abnormal laboratory findings) in subjects, users or other persons, whether or not related to the investigational medical device.

Note: This definition includes events related to the investigational medical device or the comparator. This definition includes events related to the procedures involved. For users or other persons, this definition is restricted to events related to investigational medical devices.

#### **Adverse Device Effect (ADE)**

Adverse Event related to the use of an investigational medical device

Note: This definition includes adverse events resulting from insufficient or inadequate instructions for use, deployment, installation, implantation, or operation, or any malfunction of

the investigational medical device. This definition includes any event resulting from use error or from intentional misuse of the investigational medical device.

### **Serious Adverse Event (SAE)**

Adverse Event that:

- i. leads to death;
- ii. leads to a serious deterioration in the health of the subject, that either resulted in;
  - a. a life-threatening illness or injury, or
  - b. a permanent impairment of a body structure or a body function; or
  - c. prolonged hospitalization; or,
  - d. medical or surgical intervention to prevent life-threatening illness or injury or permanent impairment to a body structure or a body function; or
- iii. led to foetal distress, foetal death or a congenital abnormality or birth defect.

Note: Planned hospitalization for a pre-existing condition, or a procedure required by the CIP, without serious deterioration in health, is not considered a serious adverse event.

### **Serious Adverse Device Effect (SADE)**

Adverse Device Effect that has resulted in any of the consequences characteristic of a Serious Adverse Event.

According to the Guidelines on Medical Devices (European Commission 2010) the above listed definitions only apply for non-CE marked devices and Conformité Européenne CE marketed devices outside the intended use. The silicone dressings used in this study are already CE marketed and are used within the intended use. Therefore formal reporting modalities do not apply. However, **(1) SAEs and (2) DD that might have led to a SAE will be reported not later than 2 calendar days to the manufacturer using the reporting form in Appendix 5.**

## **6.4 Auditing**

The trial conduct is audited by an external monitor. The following processes will be reviewed:

- Patient enrolment/patient existence
- Consent
- Eligibility
- Allocation

## 7 Ethics and dissemination

### 7.1 Research ethics approval

The trial protocol and any amendments are prepared in accordance with the Declaration of Helsinki in the version of October 1996 (48th General Assembly of the World Medical Association, Somerset West, Republic of South Africa) and according to the SPIRIT guidance (Chan et al. 2013). This protocol and the informed consent form will be reviewed and approved by the responsible ethics committee. This study involves a medical device class IIb. Because the product is CE certified already an application to the Bundesinstitut für Arzneimittel und Medizinprodukte (BfArM) is not needed (see MPG-Law § 23b). An approval to conduct the study will be obtained from the local ethics committee of the Charité-Universitätsmedizin Berlin.

This study inclusion procedure is considered ethically sound, because adverse events by applying silicone dressings at heels and the sacral skin to prevent skin ulcerations have not been reported so far (Santamaria et al. 2013a, Clark et al. 2014). Based on existing evidence it is highly probable that the intervention has positive effects in maintaining skin and tissue integrity. This is also one reason, why the use of preventive dressings is considered as one of new PU prevention strategies in the latest PU prevention and treatment guideline (NPUAP, EPUAP, PPIA 2014). Potential benefits clearly outweigh possible risks and therefore this study inclusion is justified.

### 7.2 Protocol amendments

The ethics committee will be informed about possible study amendments.

### 7.3 Consent

PU risk is highest during the first days of hospital admission. Critically ill and ICU patients are at especially high risk. Therefore it is important to start preventive interventions immediately after admission to the ED or to the ICU (within 6 hours). Patients meeting the inclusion criteria and who are able must provide written informed consent prior to participation. The informed consent form (ICF) will meet the requirements proposed by the ethics committee of the Charité. Patients being unconscious, ventilated, confused or are unable to give informed consent but meeting the inclusion criteria will be also included immediately. In that case informed consent from the legal representatives will be obtained as soon as possible. Individual consent will be sought in addition when patients subsequently regain capacity. If patients or legal representatives decide not to participate, all study data obtained so far are

deleted, the intervention will be stopped and PU preventive care procedures will be continued as usual. Any study participants or legal representatives can withdraw his or her consent at any time without giving reasons.

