**Table 1. Patient timeline**

	Admission to ED and/or ICU	Follow-up	...	End of study
Days	D0	D1	D1 + 1	D1 + x
In-/exclusion criteria	X	X		
Informed consent	X*	X*	X*	X*
Demographics	X			
Skin inspection	X	X	X	X
Randomization	X			
Application of dressings	X			
Control of dressing fit/renewal	←—————→			
All other clinical variables	X	X	X	X
Ressource use (number of dressings, wound care materials)	X	X	X	X
Adverse events monitoring and documentation	←—————→			

\*Informed consent will be sought as soon as possible after inclusion.

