### 3.6 Sample size

We are planning a study of independent cases and controls with 1 control per case. Prior data of the internal quality management indicate that the average PU incidence at the ICUs of the Charité is 0.06 per month. We expect that the cumulative PU incidence for experimental subjects will be 0.01 (RR 0.17). In order to test this hypothesis we will need to study 211 experimental patients and 211 control patients to be able to reject the null hypothesis that the PU incidence in the intervention and control groups is equal with a probability (power) of 0.8. The Type I error probability associated with this test of this null hypothesis is 0.05 (two-sided). We will use the chi-squared test statistic to evaluate this null hypothesis. To prevent a possible loss of follow-up of 10%, 464 patients in total are to be included. This total sample size is comparable to a previous trial using a similar intervention and design (Santamaria et al. 2013a). The “true” PU heel and sacral PU incidence in the study might be higher, because we will include only “high” and “very high risk” patients.

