**Figure 3. Data collection and management**

## 5.2 Statistical methods

Depending on the level of measurement (nominal, ordinal, continuous) variables will be described using absolute and relative frequencies or arithmetic means, medians and spread parameters (minimum, maximum, interquartile ranges, standard deviations). Baseline demographic (age, gender, PU risk etc.) and clinical characteristics (e.g. medical diagnoses, duration of ventilation) of each group will be displayed in a table.

The primary end point PU incidence category II, III, IV, DTI at heels and/or sacrum will be compared using a Chi-squared test. This will be the main analysis of this primary outcome. A logistic regression will be applied to adjust for baseline covariates. An alpha level of 5% (two-sided) will be applied. Kaplan-Meier analyses and logrank test will be used to compare the times to development of a new PU between groups. Multiple Cox regression analysis will be performed to adjust for potential confounders. Data will be analysed as intention to treat.

Secondary outcomes will be analysed in a similar way. Depending on the level of measurement (nominal, ordinal, continuous) secondary outcomes will be described using absolute and relative frequencies or arithmetic means, medians and spread parameters (minimum, maximum, interquartile ranges, SDs). Chi-squared or t-tests will be applied to compare groups. In case of normality assumption being violated, the Mann-Whitney U test will be used instead of t-test.

For daily measurements, missing values will be imputed via LOCF method, and the results will be compared to those without imputation.

A cost effectiveness analysis (CEA) comparing both groups will be conducted. Quantities of used preventive dressings including labor costs for application in the intervention group and quantities of used PU treatment materials (e.g. dressings, time) will be documented. Current market prizes in Euro will be used to calculate the total costs per group. An incremental cost effectiveness ratio (ICER) will be calculated by dividing the mean differences in costs by the mean differences in effects. In order to make results comparable a similar approach like the work by Santamaria et al. 2013b will be used.

All analytic steps including the CEA will be repeated for the two subgroups heel PUs and sacral PUs.

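### Section 7.3 deletes all data when deferred consent is refused after open-label randomisation, which contradicts the unqualified intention-to-treat statement in section 5.2 and can bias a comparison planned on about 15 events

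*Combined protocol and SAP*

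**What the plan says.** All of this is in the combined protocol and SAP.

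- **Section 7.3 (Consent).** Patients able to consent do so in writing before taking part. Those who are unconscious, ventilated, confused or otherwise unable are included immediately. A legal representative is approached as soon as possible, and the patient is asked again on regaining capacity. On refusal: "If patients or legal representatives decide not to participate, all study data obtained so far are" deleted, the intervention stops and usual prevention continues. Withdrawal at any time is covered in a separate sentence, which has no rule about data.
- **Table 1 (patient timeline).** Consent is marked in every column from D0 to end of study, with the footnote "Informed consent will be sought as soon as possible after inclusion".
- **Sections 4.3 and 4.4.** The next envelope is opened once screening shows eligibility. Caregivers and researchers are not blinded.
- **Section 5.2 (Statistical methods).** "Data will be analysed as intention to treat". The population is not defined further. The missing-data rule is last observation carried forward for daily measurements.
- **Section 3.6 (Sample size).** The total of 464 allows 10% for loss to follow-up, without saying whether this covers refused consent.

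**The concern.** Intention to treat means that every randomised patient is counted in the allocated arm. A patient randomised under deferred consent whose record is then deleted cannot be counted, and carrying forward a last observation does nothing for a record that no longer exists. The statistical section neither acknowledges this exception nor says how such patients are reported.

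The timing makes it more than a labelling matter. By the time consent is sought, the arm is visible: one group wears dressings and has a bedside card, the other has neither. Skin is inspected daily, so an ulcer may already be known. The decision to refuse could therefore depend on arm and on outcome. Exclusions of that kind undo the protection that randomisation gives, and with few events a small number of them can matter. The trial recruits critically ill emergency and intensive care patients, so the deferred route is unlikely to be rare.

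**Working it through.** **1. The plan's own figure.** Inputs from section 3.6: control risk 0.06 ("the average PU incidence at the ICUs of the Charité is 0.06 per month", used as a proportion), dressing risk 0.01, two-sided alpha 0.05, power 0.8, chi-squared test. With mean risk 0.035,

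n per arm = [1.960 × √(2 × 0.035 × 0.965) + 0.842 × √(0.06 × 0.94 + 0.01 × 0.99)]² / 0.05² = 210.9.

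This reproduces "211 experimental patients and 211 control patients". The total is 422 × 1.10 = 464.2, given as 464, or 232 per arm.

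**2. Planned events.** 211 × 0.06 + 211 × 0.01 = 12.7 + 2.1 = 14.8. With 232 per arm it is 13.9 + 2.3 = 16.2.

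**3. Refusal unrelated to arm and outcome.** The refusal rate is an assumption. Power is from the formula in step 1, starting from 232 per arm.

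| Refusal | Left per arm | Power |
|---|---|---|
| 0% | 232 | 0.836 |
| 10% | 209 | 0.796 |
| 20% | 186 | 0.749 |

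The expected relative risk (RR) is unchanged, so the cost is power only. A 10% refusal rate would by itself use up the whole 10% allowance.

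**4. Refusal that depends on arm and outcome.** Let f be the refusal rate among patients with an ulcer and g the rate among those without. Then

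observed risk = risk × (1 − f) / [risk × (1 − f) + (1 − risk) × (1 − g)].

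Assume a true risk of 0.06 in both arms and 10% refusal everywhere, except 30% among ulcer patients in one arm. In that arm the observed risk is 0.06 × 0.7 / (0.06 × 0.7 + 0.94 × 0.9) = 0.042 / 0.888 = 0.0473.

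- Excess in the dressing arm: RR = 0.0473 / 0.06 = 0.79.
- Excess in the control arm: RR = 0.06 / 0.0473 = 1.27.
- Exact type I error of the chi-squared test, with retained numbers at their expected 209 and 206, rises from 0.047 to 0.089.
- Under the planned effect, the same excess in the control arm cuts exact power from 0.845 to 0.647.
- The same excess in both arms leaves the null RR at 1.00.

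**5. Fragility.** Uncorrected chi-squared, X² = (difference in proportions)² / [p̄(1 − p̄)(1/n₁ + 1/n₂)], where p̄ is the pooled proportion.

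| Control | Dressing | X² | p |
|---|---|---|---|
| 13/211 | 5/211 | 3.71 | 0.054 |
| 13/211 | 4/210 (one dressing event deleted) | 4.92 | 0.027 |
| 13/211 | 2/211 (planned rates, rounded) | 8.36 | 0.004 |
| 9/207 (four control events deleted) | 2/211 | 4.71 | 0.030 |
| 8/206 (five control events deleted) | 2/211 | 3.84 | 0.0501 |

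The first row is chosen to lie near the threshold. It has 18 events rather than 15, and a dressing-arm risk of 5/211 = 2.4% against the planned 1%.

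**The case against.** Deletion on refusal may be an ethical requirement, and honouring a refusal is right. Consent is itself an inclusion criterion (section 3.2), so a patient whose consent is refused could be said never to have been eligible. The deletion rule is written for those who decline to take part, not for later withdrawal, and patients with capacity consent beforehand. All of this narrows the problem without removing it. The refusal is learned only after allocation, and section 5.2 makes no exception for it.

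Three stronger readings are tempting, and the documents do not support them.

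- **Deletions leave no trace by arm.** Section 7.3 deletes study data and does not mention allocation records. The randomisation table is made by a separate department (4.1), envelopes are sequentially numbered (4.2), and the external monitor reviews consent and allocation (6.4). The arm of a used envelope may therefore be recoverable. What is lost for certain is the outcome, and no section provides for recovering or reporting the arm.
- **Patients have no way to stop the intervention but leave their data in.** The protocol text describes none. The consent form was not available for this review and may offer one.
- **One deletion would overturn the trial.** Any test is fragile near its threshold. At the planned rates it would take five control-event deletions.

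It is also fair to say that nothing in the documents shows that refusal would depend on arm or outcome. An equal event-related excess in both arms would leave the null comparison unbiased.

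**Conclusion.** The contradiction between sections 7.3 and 5.2 stands whatever the refusal rate: for patients whose deferred consent is refused, the analysis cannot be intention to treat. It comes from a stated rule and is more than a missing detail.

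The effect on the result is a possibility, not a finding. Bias requires refusal to depend on both arm and outcome; otherwise the loss is power. The RRs of 0.79 and 1.27 and the type I error of 0.089 rest on an assumed 10% baseline refusal, an assumed 20-point excess in one arm and a 6% risk in both. The count of about 15 events assumes the planned rates, and section 3.6 itself says that the true incidence might be higher. A reader might infer that the trial's conclusion will be distorted; the documents support only that it can be, and that the plan neither reports nor bounds the exclusions. The change is worth making before data accrue, because a log of refusals has to be kept prospectively.

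**What to change.** - **Consent form.** Where it does not already offer this, and subject to ethics approval, add an option to stop the intervention and further collection while allowing data collected so far to be kept.
- **Randomisation log.** Where deletion is still requested, and again if the ethics committee agrees, keep only the envelope number, the arm and the fact of refusal.
- **Reporting.** Give the number of deleted patients by arm in the participant flow.
- **Section 5.2.** Name the primary set *all randomised patients with consent to data use* in place of plain intention to treat.
- **Sensitivity analysis.** Bound the result by counting deleted patients as best case and worst case by arm.

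The cost is an ethics amendment, one log column and one extra table, with no additional patients. Outcomes of patients who still request deletion remain lost, so the sensitivity analysis can bound that loss but not repair it.

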#### **7.4 Confidentiality**

All personal data are collected under pseudonymization. Each patient gets a distinctive subject number. The investigator administrates the subject identification list which includes the subject number as well as name, birthday, and address of the subject. The access to this is limited, only the Investigators as well as the authorized study staff, will have permission to inspect this list. All study-related information will be stored securely at the CRC. All participant information will be stored in locked file cabinets in areas with limited access. Electronical data are stored on a secured digital server of the Charité. An additional copy of the file is archived on CD-ROM together with the TMF and source data by the Charité.

#### **7.6 Access to data**

Because this is an IIS, the data is owned by the PI and therefore has full access.

#### **7.7 Ancillary and post-trial care**

Ancillary and/or post-trial care is not planned. All PU preventive and therapeutic interventions follow the clinical algorithms of the Charité-Universitätsmedizin Berlin. Trial participation will not lead to additional care.

#### **7.8 Dissemination policy**

A clinical study report will be prepared according to the ICH E3 guideline. Results will be also made available at the trial register [clinicaltrials.gov](http://clinicaltrials.gov). The study results will be presented in an international scientific journal following the guidance of the CONSORT 2010 statement (Schulz et al. 2010) and in at least one German speaking journal. Any publication will take account of the 'Uniform requirements for manuscripts submitted to biomedical journals'.

Results will be presented as posters and orally at international conferences (e.g. the Annual Meeting of the European Pressure Ulcer Advisory Panel, EWMA conference) and at national German speaking conferences (e.g. Bremer Wundkongress, Jahrestagung des Deutschen Netzwerks Evidenzbasierte Medizin, Dreiländer-Kongress für Pflege und Pflegewissenschaft).

# 9 Appendices

## Appendix 1: Standard operating procedure to apply Mepilex® Border Sacrum on intact skin

Deutsch	English
Inhaltsverzeichnis	Table of Contents

 
1. Beschreibung des Produkts
 
2. Vorbereitungen
 
3. Arbeitsschritte
 
4. Besondere Anweisungen
 
5. Mögliche Fehler/Störungen/Problem-Lösungen
 
6. Lagerbedingungen / Reinigung
 
	
 
1. Description of Device
 
2. Preparation
 
3. Workflow
 
4. Special Instructions
 
5. Possible Error/Disruptions/Problem Solutions
 
6. Storage Conditions/Cleaning
 

1. Beschreibung des Produkts
 
Mepilex® Border Sacrum ist ein Schaumverband zur Prävention und Behandlung von Dekubitus im Sakralbereich. Er ist weich, anpassungsfähig und wasserfest. Der Verbandswechsel erfolgt nahezu schmerzfrei und atraumatisch. Es verbleiben keine Rückstände auf der Haut. Der Verband wird alle 3Tage gewechselt.
	
1. Description of Device/Hardware
 
Mepilex® Border Sacrum is a special foam dressing for prevention of sacral pressure ulcer. It is very smooth, flexible/adaptable and water-resistant. Changing is nearly painless and non-traumatic.
 
Remove and replace dressing after 3 days.

Lieferumfang zum Produkt: / Delivery contents of the device:
 
Mölnlycke Health Care Mepilex® Border Sacrum
 
 
• 18x18 cm Product code: 282000
 
• 23x23 cm Product code: 282400
 
	

2. Vorbereitungen
 
Bestimmte Standards sollen vor und während der Applikation eingehalten werden.
 
a) Vorbereitung des Arbeitsplatzes:
 
 
• Legen Sie sich zwei Schaumverbände bereit,
 
• Ziehen Sie sich Handschuhe an,
 
• Legen Sie sich bei Bedarf Waschlappen und Handtuch für die optimale Reinigung des Wundauflagegebietes bereit.
 
 
b) Lagern Sie den Patienten bequem auf eine Seite, holen Sie bei Bedarf eine zweite Pflegekraft oder Lagerungsmittel zur Unterstützung.
 
c) Stellen Sie sich einen Abwurfbehälter bereit.
	
2. Preparation
 
A set of standards should be maintained before and during application.
 
a) Prepare a place/table with all material:
 
 
• Prepare two dressings,
 
• Put on gloves,
 
• For cleaning the wound area provide washcloth and towel (only if necessary)
 
 
b) Place the patient on one site (support with pillows) maybe you need help of another colleague.
 
c) Prepare a dustbin.

3. Arbeitsschritte
 
a) Inspektion des Areal. Beurteilung der Anatomie des Patienten und Entscheidung welche Applikationsform in Bezug auf Lagerung und ggf. Einschränkungen (z.B. Inkontinenz) für den Patienten in Frage kommt. (Variante A oder B in Schritt e).
	
3. Workflow
 
a) Area to protect. Assess the patient's anatomy and evaluate if the dressing should be placed according to Figure A or B based on coverage and/or potential issues with incontinence.

	

b) Stellen Sie sicher, dass die Haut frei von Dimethicone, Schutzfilmen und Salben ist. Entfernen Sie die Mitteltrennfolie des Verbandes. Das vorherige applizieren von Hautschutzprodukten ist nicht notwendig.
	
b) Ensure the skin is dry and free of dimethicone, skin sealants, emollients and remove the central release film. Use of skin barrier under dressing is not necessary.

	

c) Mit Hilfe eines Kollegen applizieren Sie den Wundverband in den Sakralbereich und der Analfalte, indem eine Gesäßhälfte leicht nach oben gezogen wird.
	
c) With assistance from a colleague, hold buttock apart. Apply dressing to sacral area and into upper aspect of gluteal cleft.

	

d) Ziehen Sie nacheinander die seitlichen Schutzfolien langsam ab und streichen Sie den Schaumverband nach außen hin aus. Überprüfen Sie, ob der Verband richtig positioniert ist sowie faltenfrei und fest an der Haut haftet.
	
d) Run side of hand along gluteal cleft to ensure secure placement. Gently smooth each side into place.

	

e) Variante A – Produktapplikation/ Figure A - Product placement.

[figure not shown]

[figure not shown]

e) Variante B – Produktapplikation/ Figure B - Product placement inverted.

f) Lagern Sie den Patienten in seitlicher Position oder auf den Rücken.
	
f) Remove the patient in a site or back position

4. Besondere Hinweise
 
a) Tägliche Überprüfung des Verbandes und Dokumentationsführung.
 
b) Achten Sie darauf, dass die Verbandränder bei Entfernung oder Erneuerung des Schaumverbandes faltenfrei, glatt und fest kleben.
 
c) Der Verbandwechsel erfolgt alle 3 Tage und so lang der Patient einem Risiko ausgesetzt ist.
	
4. Special Instructions
 
a) Daily assessment of the dressing and documentation.
 
b) Removal and reapplication of dressing. Ensure the border of the dressing is smooth/even with no wrinkles.
 
c) Remove and replace dressing after 3 days as long as the patient is still at risk.

5. Mögliche Störungen / Problemlösungen
 
a) Die Auflagefläche muss trocken und frei von Pflegeprodukten und eventuellen Pflasterresten sein, damit der Schaumverband gut auf der Haut haftet.
 
b) Keine zusätzlichen Pflegeprodukte verwenden.
	
5. Possible Error / Problem Solutions
 
a) The application area must be dry and free of dimethicone, skin sealants, emollients and remove the center release film for good adhesion.
 
b) Don't use any other additional products.

6. Lagerung und Reinigung
 
a) Gestalten Sie Ihren Arbeitsplatz übersichtlich und sauber.
 
b) Lagern Sie die Wundverbände (Mepiplex® Border Sacrum) trocken und bei Raumtemperatur.
	
6. Storage Conditions/Cleaning
 
 
• Clean and tidy up your workplace
 
• Store the dressings Mepiplex® Border Sacrum at room temperature in a dry place.
 

